10.4.4 Secondary efficacy analysis

Secondary endpoints are as follows:

- 1. Percentage of subjects with HbA1c < 6.5% at Week 8 and 12.
- 2. Percentage of subjects with HbA1c < 7% at Week 8 and 12.
- 3. Changes in fasting blood glucose from baseline at Week 4, 8, and 12.
- 4. Changes in postprandial blood glucose from baseline at Week 8 and 12.
- 5. Changes in fasting insulin level from baseline at Week 4, 8, and 12.
- 6. Changes in postprandial insulin level from baseline at Week 8 and 12.
- 7. Changes in fasting C-peptide from baseline at Week 4, 8, and 12.
- 8. Changes in postprandial C-peptide from baseline at Week 8 and 12.
- 9. Changes in serum ALT, AST, GGT, and TBIL from baseline at Week 4, 8, and 12.
- 10. Changes in CAP measured by liver transient elastography from baseline with 12-week treatment.
- 11. Changes in C-reactive protein from baseline with 12-week treatment.
- 12. Changes in serum LDL-C, HDL-C, TG, and TC from baseline at Week 4, 8, and 12.

- 13. Changes in body weights of subjects from baseline at Week 4, 8, and 12.
- 14. Changes in medication for blood lipid control in subjects from baseline with 12-week treatment.

Protocol No.: HTD1801.PCT103

For the measurement data in the secondary efficacy endpoints, the same analysis method as the primary efficacy endpoints is used, with the random stratification factors in the model: CAP and HbA1c; for the enumeration data in the secondary efficacy endpoints, invalid filling is applied and the CMH method is used for inter-group comparison, with the random stratification factors in the model: CAP and HbA1c.

Study Objectives	Endpoints	Estimated Objective	
Primary objective: to evaluate the effect of HTD1801 on glycemic control in T2DM patients.	Primary endpoint: changes in HbA1c from baseline with 12-week treatment.	Primary Estimated Objective Population: according to the ITT principle, including all subjects who have been randomized in the study and used the investigational drug at least once. Therapy: randomly assigned therapy (see Section 4.1 for details) and possible salvage therapy (see Section 3.3.2 for details) Endpoint: see the left column Concomitant event and treatment strategies: for concomitant event of the salvage therapy, the therapy strategy should be applied, i.e., the data after salvage therapy should also be included in the analysis Summary at population level: the least-squares means inter-group differences should be calculated using MMRM and the ANCOVA model of LOCF (see Section 10.4.3 for details) Secondary Estimated Objective Population: according to the ITT principle, including all subjects who have been randomized in the study and used the investigational drug at least once Therapy: randomized therapy (see Section 4.1 for details) and possible salvage therapy (see Section 3.3.2 for details) Endpoint: see the left column Concomitant event and treatment strategies: for concomitant event of the salvage therapy, the on-treatment strategy should be applied, i.e., the data after salvage therapy should also be included in the analysis Summary at population level: the least-squares mean inter-group differences should be calculated using MMRM and the ANCOVA model of LOCF (see Section 10.4.3 for details)	
	Secondary measurement endpoints: see Section 10.4.4 for details.	Primary Estimated Objective Population: according to the ITT principle, including all subjects who have been randomized in the study and used the investigational drug at least once. Therapy: randomly assigned therapy (see Section 4.1 for details) and possible salvage therapy (see Section 3.3.2 for details) Endpoint: see the left column Concomitant event and treatment strategies: for concomitant event of the salvage therapy, the therapy strategy should be applied, i.e., the data after salvage therapy should also be included in the analysis Summary at population level: the least-squares means inter-group differences should be calculated using MMRM and the ANCOVA model of LOCF (see Section 10.4.3 for details) Secondary Estimated Objective Population: according to the ITT principle, including all subjects who have been randomized in the study and used the investigational drug at least once Therapy: randomized therapy (see Section 4.1 for details) and possible salvage therapy (see Section 3.3.2 for details) Endpoint: see the left column Concomitant event and treatment strategies: for concomitant event of the salvage therapy, the on-treatment strategy should be applied, i.e., the data after salvage therapy should also be included in the analysis	

		Summary at population level: the least-squares means inter-group differences should be calculated using MMRM and the ANCOVA model of LOCF (see Section 10.4.3 for details)
	Secondary metric endpoints: see Section 10.4.4 for details.	Primary Estimated Objective Population: according to the ITT principle, including all subjects who have been randomized in the study and used the investigational drug at least once. Therapy: randomly assigned therapy (see Section 4.1 for details) and possible salvage therapy (see Section 3.3.2 for details) Endpoint: see the left column Concomitant event and treatment strategies: for concomitant event of the salvage therapy, the therapy strategy should be applied, i.e., the data after salvage therapy should also be included in the analysis Summary at population level: CMH method is used after invalid filling applied to calculate inter-group differences (see Section 10.4.3 for details) Secondary Estimated Objective Population: according to the ITT principle, including all subjects who have been randomized in the study and used the investigational drug at least once. Therapy: randomly assigned therapy (see Section 4.1 for details) and possible salvage therapy (see Section 3.3.2 for details) Endpoint: see the left column Concomitant event and treatment strategies: for concomitant event of the salvage therapy, the on-treatment strategies: for concomitant event of the salvage therapy should also be included in the analysis Summary at population level: CMH method is used after invalid filling applied to calculate inter-group differences (see Section 10.4.3 for details)
Safety endpoints	Safety endpoints: see Section 10.4.5 for details.	Estimated Objective Population: including all subjects who have been randomized and used the investigational drug at least once following by at least one subsequent safety assessment. Therapy: actually assigned therapy and possible salvage therapy (see Section 3.3.2 for details) Endpoint: see the left column Concomitant event and treatment strategies: for concomitant event of the salvage therapy, the therapy strategy should be applied, i.e., the data after salvage therapy should also be included in the analysis Summary at population level: the incidence is calculated for safety endpoints, and the chi-square test is used (Fisher's exact test is used based on the data) for inter-group comparison if necessary.

Protocol No.: HTD1801.PCT103

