10.4.3 Primary efficacy analysis

The efficacy analysis is mainly based on the FAS, and the statistical analysis is based on the PPS. The efficacy analysis is mainly based on the therapy strategy, with the on-treatment strategy as the sensitivity analysis.

The primary efficacy endpoint is the change in HbA1c from baseline with 12-week treatment. For the primary efficacy endpoint, the mixed model repeated measures (MMRM) for repeated measurement data is used for analysis, with the change in HbA1c from baseline as the dependent variable, the treatment group, measurement time point, random stratification factor (CAP≥274 dB/m or CAP < 274 dB/m) as the independent variables, and subjects' baseline HbA1c as a covariate. Judgments are made based on model-adjusted least-squares means between-group differences. Sensitivity analysis is performed using an analysis of covariance (ANCOVA) model with the last measurement carried forward (LOCF) for subjects who withdrew from the study before 12 weeks.

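### The on-treatment estimand carries the same post-salvage rule as the primary estimand, so the on-treatment sensitivity analysis cannot show the influence of salvage

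*Protocol*

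**What the plan says.** Protocol Section 10.4.3 (and the synopsis) sets the hierarchy: "The efficacy analysis is mainly based on the therapy strategy, with the on-treatment strategy as the sensitivity analysis". It also plans an ANCOVA with LOCF for subjects who leave before 12 weeks, and use of the per-protocol set.

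The estimand table in Section 10.4.4 gives each efficacy row a primary and a secondary estimand. Salvage is the only intercurrent event it names. For HbA1c change, the primary estimand reads "the therapy strategy should be applied, i.e., the data after salvage therapy should also be included in the analysis" and the secondary reads "the on-treatment strategy should be applied, i.e., the data after salvage therapy should also be included in the analysis". The row for the continuous secondary endpoints repeats both clauses. In the row analysed by CMH, the secondary estimand reads "the on-treatment strategies: for concomitant event of the salvage therapy should also be included in the analysis".

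**The concern.** A sensitivity analysis to a treatment-policy analysis is informative only if it treats the intercurrent event differently. Here the name changes but the rule does not.

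The event matters for interpretation. Salvage is a glucose-lowering drug added to study drug (Section 5.1.3.3), and subjects in whom it succeeds stay on it and in the study (Section 3.3.2.2). A Week 12 HbA1c can therefore contain its effect. In a proof-of-concept, dose-finding trial, readers will want to know how far the contrasts with placebo depend on salvage. If the two analyses are reported side by side, their agreement could be taken as robustness when the definitions guarantee it.

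**Working it through.** **Scale of the effects.** Section 10.2 assumes changes of -1.1, -1.4 and -0.4 points (500 mg BID, 1000 mg BID, placebo), SD 1.1, 27 evaluable subjects per group and two-sided alpha 0.05. The differences from placebo are 0.7 and 1.0. The standard error is 1.1 × √(2/27) = 0.299.

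- Difference 1.0: 1.0/0.299 = 3.34. Power is 91.6% (normal) or 90.6% (noncentral t, 52 df). The protocol states 90%.
- Difference 0.7: 0.7/0.299 = 2.34. Power is 64.7% (normal) or 63.1% (t). The protocol states 63%.

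The protocol's figures reproduce and are not in question.

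**The two estimands for HbA1c change, side by side (Section 10.4.4).**

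| Attribute | Primary | Secondary |
|---|---|---|
| Population | "including all subjects who have been randomized in the study and used the investigational drug at least once" | the same |
| Treatment | "Therapy: randomly assigned therapy (see Section 4.1 for details) and possible salvage therapy (see Section 3.3.2 for details" | "Therapy: randomized therapy (see Section 4.1 for details) and possible salvage therapy (see Section 3.3.2 for details" |
| Endpoint | HbA1c change | the same |
| Salvage rule | post-salvage data included | post-salvage data included |
| Summary | "inter-group differences should be calculated using MMRM and the ANCOVA model of LOCF (see Section 10.4.3 for details" | the same |

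Only the strategy label differs. The same subjects, values and models give the same estimates, so primary minus on-treatment is exactly 0 for the MMRM and exactly 0 for the LOCF ANCOVA, at any salvage rate. The comparison comes out the same for the continuous secondary endpoints. No section of the protocol excludes, censors or resets a post-salvage efficacy value.

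**CMH row.** The words that should link the strategy to the data are missing from the secondary estimand. What is left ends with inclusion in the analysis, so it probably matches the other rows, but the text is too damaged to be certain.

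**What the analysis would fail to show.** To first order, the shift in a treatment contrast is

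shift = (placebo salvage rate − active salvage rate) × HbA1c effect of salvage by Week 12.

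The protocol gives none of these three quantities. The following are assumptions for illustration:

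- Placebo 5%, active 0%, effect 0.5: 0.05 × 0.5 = 0.025 points.
- Placebo 20%, active 0%, effect 0.8: 0.20 × 0.8 = 0.16 points, which is 0.16/0.7 = 23% of the 500 mg contrast and 0.16/1.0 = 16% of the 1000 mg contrast.
- Placebo 20%, active 10%, effect 0.8: 0.10 × 0.8 = 0.08 points.
- Equal rates: 0.

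The range 0.025 to 0.16 holds only if no active-arm subject is salvaged and the full effect is present by Week 12. Section 3.3.2.2 allows for subjects with less than 4 weeks of salvage at the last treatment visit, so for the salvage rates and effects assumed here 0.16 is an upper figure.

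**The case against.** The strongest reply is that this is a copied clause or a translation slip: the label shows the intent, and the SAP, due before database lock (Section 10.1), will settle it. That is likely, but it does not cure the text. The protocol does not leave the rule open. It states one, and the rule contradicts its label. A SAP that follows the rule inherits the problem, and one that departs from it conflicts with the protocol.

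A second reply is that on-treatment may mean while still taking study drug, with salvage allowed. But salvage is the only event the table names, so the strategy has to describe how salvage is handled. That reading would also separate the analyses very little. Early discontinuers are asked back for a withdrawal visit within a week (Section 3.3), after which only a safety follow-up is planned, by telephone (Section 4.3.8).

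Parts of the opposing case do stand, and they rule out several stronger readings:

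- A reader might infer that the whole sensitivity plan is empty. It is not. LOCF for early withdrawals and the per-protocol analysis are still different analyses.
- A reader might infer that someone who reaches an HbA1c target only after salvage certainly counts as a success under both estimands. The CMH row is too garbled to establish that.
- A reader might infer that the primary result is wrong by up to 0.16 points. Including post-salvage data is what a treatment-policy estimand does, and the protocol nowhere says that salvage will be commoner on placebo.
- A reader might infer that the planned invalid filling already makes salvaged subjects non-responders. Section 10.4.4 does not link it to salvage.

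**Conclusion.** The point holds for the primary endpoint and the continuous secondary endpoints, and probably for the CMH row. As written, the on-treatment analysis reproduces the primary-estimand results exactly and cannot show what salvage contributes. That conclusion follows from the text and needs no assumption about salvage rates. The dilution figures are illustrations only.

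The primary estimand, its model and the sample size are untouched, and the trial is exploratory with no alpha correction. The defect lies in a supportive analysis and can be corrected before database lock. It should be fixed, but it does not threaten the main result.

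**What to change.** In each efficacy row of the Section 10.4.4 table, change the secondary estimand as follows:

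1. Replace the salvage clause so that efficacy values collected after the first dose of salvage drug are excluded, and remove salvage from the treatment attribute.
2. For the MMRM, set scheduled visits after the start of salvage to missing. Post-baseline HbA1c is scheduled only at Weeks 8 and 12, so a subject salvaged before Week 8 may have no scheduled value. Because a pre-salvage visit can replace the Week 8 visit when it falls within 7 days of it (Section 4.3.9), say whether its value then counts as Week 8.
3. For the LOCF ANCOVA, carry forward the last pre-salvage value, including the one from the pre-salvage visit, where HbA1c is already collected (Section 4.3.9). That visit has no standard meal, so postprandial endpoints fall back on an earlier scheduled value.
4. For HbA1c below 6.5% and below 7%, restore the garbled text and state how salvaged subjects are classified. If they are to be non-responders, name that as a composite strategy.

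The table names no intercurrent event other than salvage, and this correction does not require adding one. The cost is wording in three rows and a second run of the efficacy models across the primary and secondary endpoints. No new data collection is needed.

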10.4.5 Safety data analysis

Based on the SS, the safety analysis is performed based on the therapy strategy.

AEs

All AEs are coded by MedDR SOC and PT. The number and percentage of AEs, such as AEs, drug-related AEs, SAEs, and other major medical events, are calculated separately, and a detailed list is provided. The incidence is calculated with the number of subjects in SS in each group as the denominator, and the chi-square test is used (Fisher's exact probability method is used based on the data) for inter-group comparison if necessary.

Hypoglycemia event

The number of subjects, percentage and number of cases of hypoglycemia events (Grade 1 hypoglycemia event, Grade 2 hypoglycemia event, Grade 3 hypoglycemia event, etc.) are analyzed.

Clinical laboratory tests

Including hematology, blood biochemistry, urinalysis and coagulation tests.

The visit results of each laboratory test and their changes from baseline are described with mean, standard deviation, median, minimum and maximum.

Protocol No.: HTD1801.PCT103

The clinical judgment results (normal, abnormal with no clinical significance, abnormal with clinical significance, and not tested) of the laboratory results before and after treatment are presented in cross tabulation.

For subjects with abnormal laboratory results during the double-blind treatment phase, the results of each examination and judgment are listed according to the abnormality with clinical significance and the abnormality without clinical significance.

Evaluation on vital signs

The results of vital signs in each visit each and their changes from baseline are described with mean, standard deviation, median, minimum and maximum.

Evaluation on physical examination

The physical examination results of each visit are described, the number of normal and abnormal subjects and percentages are calculated, and abnormal values are listed.

Evaluation on ECG

Refer to the evaluation of laboratory test indicators.

10.4.6 Pharmacokinetic analysis

The data on blood samples collected in the morning under fasting conditions on V4, and before the first dose of on the day of V5, V6, and V7 are summarized to evaluate the trough concentration of multiple-dose HTD1801 in T2DM subjects, and descriptive statistics of the trough concentration are performed.

10.4.7 Population pharmacokinetic analysis

See the separate PPK analysis plan for details.

10.4.8 Intestinal flora analysis

For details, see the separate analysis plan for intestinal flora.

11. CLINICAL STUDY MANAGEMENT

11.1 Statement

This clinical study will be conducted in accordance with the standard operating procedures of the Sponsor and CRO, to ensure that the study complies with the *Declaration of Helsinki*, *E6 Guidelines for Good Clinical Practice* issued by International Council for Harmonisation of Technical Requirements for Pharmaceuticals for Human Use (ICH), *NMPA GCP*, and clinical study regulations.

Protocol No.: HTD1801.PCT103

When the investigator signs the protocol, he agrees to conduct the study in strict accordance with the protocol, GCP, and relevant laws and regulations, and keep all the information provided by the Sponsor in accordance with confidentiality requirements.

11.2 Ethical Part

This study is designed and prepared on the basis of the *Declaration of Helsinki* by the World Medical Association, taking into account the rights and welfare of the subjects. Principal investigator or investigators of the study should explain the objectives of the study and all potential possibilities to the subject. Only subjects who voluntarily agree to participate in the clinical study and sign the ICFs can be enrolled.

Investigators and researchers participating in the study should correctly understand and be familiar with the study protocol, and be able to prepare measures in advance, such as response measures for SUSAR, required reports and adequate training. Clinical investigators must comply with the *Declaration of Helsinki*, *E6* issued by ICH, GCP issued by NMPA and relevant regulations.

Principal investigator and the personnel participating in the study should abide by the study protocol to conduct the study scientifically with the currently recognized technology.

According to the policies and regulations of China, investigators need to provide relevant documents to the ethics committee.

Before the start of the clinical study, the approval from the ethics committee and the drug regulatory authority must be obtained.

The modification of the study protocol needs to be submitted to the ethics committee for approval, and the drug regulatory authority should be notified according to local requirements.

For any clinical safety-related SAE or SUSAR during the clinical study that may affect the safety of the subjects and the implementation of the study, the investigator must inform the Ethics Committee.

The completion of the study should be notified to the ethics committee.

11.3 Original Record Verification

The investigator must properly handle all data obtained during clinical study to ensure the rights and privacy of subjects included in clinical study. The investigator must agree to the CRA/auditor/inspector to view and review the required clinical study data in order to verify the accuracy of the raw data and understand the study schedule. If the original records cannot be verified, investigators should agree to assist the monitors/auditors/inspectors to further confirm the quality control of the data.

11.4 Quality Assurance and Audit

All drugs and materials used in the study are premised on the basis of quality control. The Sponsor and authorized personnel or related medical regulatory authorities have the right to review the

study, the purpose of which is to ensure the authenticity of clinical study data and the compliance with the study protocol.

Protocol No.: HTD1801.PCT103

This study will be organized, carried out and reported in accordance with the study protocol and standard operating procedures of the Sponsor and CRO. In ICH E6, quality assurance (QA) is defined as "All planned and systematical actions that are established to ensure that the study is performed and the data are generated, documented (recorded), and reported in compliance with GCP and applicable regulatory requirement(s)". The Sponsor's QA work will be carried out in accordance with the study audit plan. Section 5.19.3(b), ICH E6 states that the audit plan and the study audit process should be established under the governance by the importance of the study in the submissions to the competent authority, the number of subjects included in the study, study type and complexity, the risk level to subjects in the study, and any issues identified. QA work can be outsourced to a CRO or an independent consultancy. Investigators are required to support the audit, attend the audit activities as required by the auditor, and allow the auditor to directly access the original data/documents, including all medical records, study-related documents and mails, and the informed consent documents of the study. Subjects will be informed of the inspection or audit process of the study, but their privacy and data will be strictly protected.

11.5 Informed Consent Form (ICF)

Investigators are responsible for explaining to each subject the purpose, methods, benefits and potential risks of the study, alternative treatment methods, rights and obligations of subjects in accordance with the *Declaration of Helsinki*; subjects should be informed that they have the right to withdraw from the study at any time without compromising their personal interests. ICFs signed by the subject must be obtained before any operating procedures related to the study.

Oral explanations must be made when giving written ICFs to subjects. The ICFs must be dated and signed by each subject or his/her legal guardian or impartial witness. The signed ICF (including information page) should be kept by the subject in duplicate, and the other signed ICF should be kept by the study site as a study file.

The ICFs must be agreed and signed by the subjects or their legal guardian or impartial witness before any study-related process begins. Before obtaining the ICFs, investigators or their designees should provide subjects with sufficient time and opportunity to ask for details about the study and to decide whether to participate in the study. The informed consent process should be documented in the course record or study medical record on the day of the screening visit.

The investigator is responsible for the informed consent process. If any information about the subject's willingness to continue participating in the study is obtained during the study, the ICFs must be updated and given to the subject to confirm the subject's willingness to continue participating in the study. The revised ICFs should be provided to subjects with the ethical approval.

By signing the ICFs, the subject must also agree to allow the Sponsor, the NMPA, the auditor and/or the clinical study monitor authorized by the Sponsor to access the raw data of the study. Reviewers must abide by the confidentiality statement.

